4.1. Protocol Deviations

Significant protocol deviations (including deviations related to study inclusion/exclusion criteria, conduct of the trial, participant management or participant assessment) will be summarized and listed. Separately, significant deviations which result in exclusion from analysis populations and events that result in exclusion from analysis populations will be summarized and listed.

Protocol deviations will be tracked by the study team throughout the conduct of the study in accordance with the Protocol Deviation Management Plan, entitled Study Deviation Tool and Rules.

- Data will be reviewed prior to freezing the database to ensure all significant deviations and deviations which may lead to exclusion of a participant from the analysis populations are captured and categorized in the protocol deviations dataset. This will occur prior to unblinding.
- This dataset will be the basis for the summaries and Listings of significant protocol deviations.

A separate Listing of all inclusion/exclusion criteria deviations will also be provided. This Listing will be based on data as recorded on the inclusion/exclusion page of the eCRF.

5. CONSIDERATIONS FOR DATA ANALYSES AND DATA HANDLING CONVENTIONS

5.1. Study Treatment & Subgroup Display Descriptors

Randomized and actual treatment will be reported per [Table 4](#). This accounts for potential treatment misallocations due to double-dummy treatments, if applicable.

Table 4 Randomized and Actual Treatment Group Descriptions

Randomized Treatment Group Descriptions			
Randomized Treatments (double-dummy)		Data Displays for Reporting	
Tablet	Capsule	Description	Order in TFL
Gepotidacin	Placebo (matched to Nitrofurantoin)	Gepotidacin 1500 mg BID	1
Placebo (matched to Gepotidacin)	Nitrofurantoin	Nitrofurantoin 100 mg BID	2
Actual Treatment Group Descriptions (Listing of actual and randomized treatment)			
Actual Treatments (double-dummy)		Data Displays for Reporting	
Tablet	Capsule	Description	Order in TFL
Placebo (matched to Gepotidacin)	Placebo (matched to Nitrofurantoin)	Placebo	1
Gepotidacin	Nitrofurantoin	Gepotidacin 1500 mg BID + Nitrofurantoin 100 mg BID	2
Gepotidacin	Placebo (matched to Nitrofurantoin)	Gepotidacin 1500 mg BID	3
Placebo (matched to Gepotidacin)	Nitrofurantoin	Nitrofurantoin 100 mg BID	4
Actual Treatment Group Descriptions (Safety TFL)			
Actual Treatments (double-dummy)		Data Displays for Reporting¹	
Tablet	Capsule	Description	Order in TFL
Placebo (matched to Gepotidacin)	Placebo (matched to Nitrofurantoin)	Placebo	1
Gepotidacin	Nitrofurantoin	Gepotidacin 1500 mg BID	2

Randomized Treatment Group Descriptions			
Gepotidacin	Placebo (matched to Nitrofurantoin)	Gepotidacin 1500 mg BID	2
Placebo (matched to Gepotidacin)	Nitrofurantoin	Nitrofurantoin 100 mg BID	3

1. Safety Summaries will include “Gepotidacin 1500 mg BID” and “Nitrofurantoin 100 mg BID” arms only, all other data will be listed only

Total (across all treatment groups) will be presented for study population, safety, and selected microbiology displays.

[figure not shown]
5.2. Baseline Definitions

For all endpoints, the baseline value will be the latest predose assessment with a non-missing value (or randomization date in participants who are randomized but did not receive study treatment), including those from unscheduled visits. If time is not collected, Day 1 assessments are assumed to be taken prior to first dose and used as baseline. For clinical signs and symptoms assessments, CCI and microbiological assessments, all Day 1 symptom assessments and urine samples (collected for identification of uropathogens) are used as baseline regardless of if they were taken pre or post dose. Urine samples collected on Day -1 or Day 1 can be considered as baseline. If baseline data is missing, then change from baseline calculations will not be performed and will be set to missing.

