- For the primary efficacy endpoint of therapeutic response (combined per-participant microbiological and clinical response), therapeutic success refers to participants who have been deemed both a microbiological success (reduction of all qualifying bacterial uropathogens [e.g., $\geq 10^5$ CFU/mL; defined in [Appendix 4](#)] recovered at Baseline to $< 10^3$ CFU/mL as observed on quantitative urine culture without the participant receiving other systemic antimicrobials) and a clinical success (resolution of signs and symptoms of acute cystitis present at Baseline [and no new signs and symptoms] without the participant receiving other systemic antimicrobials) at the TOC Visit in the Microbiological Intent-to-Treat Nitrofurantoin-Susceptible (micro-ITT NTF-S) Population, regardless of treatment discontinuation. The TOC Visit is 10 to 13 days after randomization, which is also 5 to 8 days after completion of study treatment.
- Participants may return to the study site at any time due to AEs or if they are experiencing new or continuing signs and symptoms of acute cystitis. Participants will be assessed and treated per the investigator's judgement. If a participant is switched to a different antibiotic before or during the TOC Visit, all TOC procedures should be completed before the other antibiotic is started.

- Participants with a concomitant fungal infection can only be treated with topical antifungals per local standard of care.
- Participants will return to the study site on Day 28 (± 3) for a Follow-up Visit. Participants experiencing signs and symptoms suggestive of infection recurrence or relapse will be assessed and treated per the investigator's judgement.
- The duration of study participation is approximately 28 days with 4 planned study visits (see Section 8 for study visit details):
 - Baseline (Day 1) Visit
 - On-therapy (Day 2 to 4) Visit
 - TOC (Day 10 to 13) Visit
 - Follow-up (Day 28 ± 3) Visit

A study design schematic is depicted in [Figure 1](#). The Schedule of Activities (SoA) is provided in [Section 1.3](#).

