Note: For all study visits, to minimize the amount of time that participants spend at the clinic, eConsent may be utilized and remote collection of study-related data may be obtained as described in the SRM. Thus, some visit data may be collected through a combination of telemedicine and on-site visits. Collection of information via telemedicine will be performed only where local regulations permit.

- **Baseline (Day 1) Visit:** The Baseline Visit will be performed before dosing on Day 1. Assessments will be performed as shown in in the SoA (Section 1.3), including the following:
 - Pretreatment baseline specimens for microbiological testing will be collected, as described in Section 8.1.1. Clinical signs and symptoms of acute cystitis will be recorded, as described in Section 8.1.3.1 and Appendix 6. [REDACTED]
 - Following completion of all pretreatment assessments, eligible participants will be randomly assigned to a study treatment, as described in Section 6.3.
 - The first dose of randomly assigned oral study treatment will be administered at the study site. After dose administration, Day 1 posttreatment assessments will be performed, as shown in Section 1.3. Any AEs or clinically significant

changes should be followed accordingly. Subsequent to administration of the first dose at the study site, participants will self-administer doses as outpatients thereafter, beginning with the second dose. (Note: Each dose should be taken after food consumption and with water.)

- The On-therapy, TOC, and Follow-up Visits should be scheduled before the participant leaves the study site on Day 1 (as per the Schedule of Activities Table in Section 1.3); the planned return day/time should be at the convenience of the participant and also the availability of the study site staff.
- **On-therapy (Day 2 to 4) Visit:** Participants will be instructed to return to the study site 1 to 3 days following study treatment administration at Baseline in order to complete the On-therapy Visit. Assessments will be performed as shown in the SoA (Section 1.3), including the following:

- The On-therapy Visit will be preceded by a documented reminder contact from the study site to the participant 24 ± 4 hours before the scheduled appointment time per the method (e.g., text message, telephone call, e-mail) confirmed with the study site staff prior to departing the study site on Day 1.

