8.1.2. Bacteriology Samples

At the Baseline Visit, a pretreatment, clean-catch midstream urine sample must be obtained from all randomized participants for Gram stain, quantitative bacteriological culture, and in vitro antimicrobial susceptibility testing at a designated central

laboratory(ies). For inclusion in the micro-ITT Population, a baseline qualifying bacterial uropathogen is required as defined in [Appendix 4](#); for inclusion in the micro-ITT NTF-S Population, the baseline qualifying uropathogen must also be susceptible to nitrofurantoin. At the On-therapy, TOC, and Follow-up Visits, a clean-catch midstream urine sample will be obtained and sent to a designated central laboratory(ies) for Gram stain, quantitative bacteriological culture, and in vitro antimicrobial susceptibility testing. Identification and susceptibility testing of isolates recovered from urine specimens at all visits will also be conducted at a designated central laboratory(ies). Additional tests, as needed, to further characterize recovered isolates will also be performed by a designated central laboratory(ies). Instructions for sample collection, processing, and shipment are provided in the SRM and the laboratory manual. The study site should follow the Microbiology Procedures section of the laboratory manual to minimize potential contamination of the specimens.

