9.3. Populations for Analyses

For purposes of analysis, the following populations are defined:

Population	Description
Intent-to-Treat (ITT) Population	All participants randomly assigned to study treatment. Participants will be analyzed according to their randomized study treatment.

Population	Description
Microbiological ITT (micro-ITT) Population	All participants randomly assigned to study treatment who receive at least 1 dose of study treatment and have a qualifying baseline uropathogen (defined in Appendix 4), from a quantitative bacteriological culture of a pretreatment clean-catch midstream urine specimen. Participants will be analyzed according to their randomized study treatment.
Micro-ITT NTF-S Population	All participants in the micro-ITT Population whose baseline qualifying bacterial uropathogens all are susceptible to nitrofurantoin (NTF-S). Participants with missing MIC susceptibility results for any qualifying uropathogens will not be included in the NTF-S subpopulation. Participants will be analyzed according to their randomized study treatment. This is the primary analysis population.
Micro-ITT NTF-NS Population	All participants in the micro-ITT Population who have any qualifying baseline bacterial uropathogens that are not susceptible to nitrofurantoin (NTF-NS), defined as resistant to nitrofurantoin, intermediate to nitrofurantoin, or have no interpretation to nitrofurantoin. Participants with missing MIC susceptibility results for all qualifying uropathogens will not be included in the NTF-NS subpopulation. Participants will be analyzed according to their randomized study treatment.
Microbiologically Evaluable (ME) Population	Participants who meet the definition of the micro-ITT Population, follow important components of the study (as specified in the RAP) and have an interpretable quantitative urine culture at the specified visit. Note: Visit-specific ME populations will be defined in the RAP.
ME NTF-S Population	All participants in the ME visit-specific population whose baseline qualifying bacterial uropathogens all are susceptible to nitrofurantoin (NTF-S). Note: Visit-specific ME NTF-S populations will be defined in the RAP.
ME NTF-NS Population	All participants in the ME visit-specific population who have any baseline qualifying bacterial uropathogens that are not susceptible to nitrofurantoin (NTF-NS). Note: Visit-specific ME NTF-NS populations will be defined in the RAP.

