4. ANALYSIS POPULATIONS

Population	Definition / Criteria	Analyses Evaluated
Screened Population	
 All participants who were screened for eligibility Participants will be analyzed according to their randomized study treatment. 	
 Study Population
Intent-to-Treat (ITT) Population	
 All participants randomly assigned to study treatment. Participants will be analyzed according to their randomized study treatment. 	
 Study Population Efficacy
Microbiological ITT (micro-ITT) Population	
 All participants randomly assigned to study treatment who receive at least 1 dose of study treatment and have a qualifying baseline uropathogen from a quantitative bacteriological culture of a pretreatment clean-catch midstream urine specimen. Participants will be analyzed according to their randomized study treatment. 	
 Study Population Efficacy
micro-ITT NTF-S Population	
 All participants in the micro-ITT Population whose baseline qualifying uropathogens are all susceptible to nitrofurantoin (NTF-S)¹. Participants with missing MIC susceptibility results for any qualifying uropathogens will not be included in the NTF-S sub-Population. Participants will be analyzed according to their randomized study treatment. 	
 Study Population Efficacy (including the primary efficacy analysis if the study does not stop for efficacy)
micro-ITT NTF-S (IA Set) Population	
 All participants in the micro-ITT NTF-S Population who, per the interim analysis data, had: 
 the opportunity to reach their Test of Cure (TOC) visit, or had not yet reached their TOC visit, but were already known to be failures (e.g., subjects who took other systemic antimicrobial or withdrew from the study before the TOC visit) Participants will be analyzed according to their randomized study treatment. 
Note: this population will only be used as the primary analysis population if the study stops for efficacy.²
	
 Study Population Efficacy (including the primary efficacy analysis if the study stops for efficacy)

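### SAP 5.2 lets a documented post-dose Day 1 urine culture count as baseline, although the micro-ITT populations, and so the primary population, require a pretreatment specimen

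*SAP*

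**What the plan says.** SAP 5.2 opens with a conventional rule: "For all endpoints, the baseline value will be the latest predose assessment with a non-missing value". Day 1 records without a time are assumed to precede the first dose. It then makes an exception for Day 1 symptom assessments and urine cultures; for the latter, "urine samples (collected for identification of uropathogens) are used as baseline regardless of if they were taken pre or post dose". Urine from Day -1 is also allowed.

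SAP Section 4 defines micro-ITT as treated participants who "have a qualifying baseline uropathogen from a quantitative bacteriological culture of a pretreatment clean-catch midstream urine specimen". The primary population is a subset of this: "All participants in the micro-ITT Population whose baseline qualifying uropathogens are all susceptible to nitrofurantoin". Protocol 9.3 uses the same condition, a qualifying uropathogen "from a quantitative bacteriological culture of a pretreatment clean-catch midstream urine specimen", and Protocol Appendix 4 repeats it. Protocol 8.1.2 makes it a collection requirement: "At the Baseline Visit, a pretreatment, clean-catch midstream urine sample must be obtained from all randomized participants". Protocol Section 8 places the visit itself ahead of treatment: "The Baseline Visit will be performed before dosing on Day 1".

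The exception does not appear in SAP 2.1, which lists the changes from the protocol's planned analysis. None of the five sensitivity analyses in SAP 7.1.6.2 removes participants whose baseline culture is post-dose.

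**The concern.** Entry to the primary population is decided by a culture result. If the culture was taken before the first dose, the result cannot depend on the assigned drug, and restricting to culture-positive participants preserves the randomised comparison. If it was taken after the first dose, the result may depend on that drug. A participant whose count falls quickly may drop below the qualifying level and be left out, while one who responds slowly stays in. If this happens at different rates in the two arms, the retained participants are no longer comparable. Blinding does not prevent it, because the selection acts through the drug and not through anyone's knowledge of it.

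The mechanism is plausible on the documents' own information. Protocol 4.3 reports about 287 mg of unchanged gepotidacin excreted in urine after a single 1500 mg dose. The protocol gives 10^5 CFU/mL as its example of a qualifying count, and SAP 11.4.4 reports counts in tenfold bands, so a fall of one band can change a participant's status.

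**Working it through.** **1. Does the exception cover only samples of unknown timing?** No. SAP 5.2 already treats untimed Day 1 records as predose. The exception adds something only for samples known to be post-dose. These should be identifiable: Protocol 1.3 and 6.4 require the time of on-site doses to be recorded, and SAP 2.4 judges antimicrobial use against the TOC urine culture to the minute.

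**2. Do the two rules give different answers?** Take a participant whose only Day 1 urine is documented as post-dose and grows a nitrofurantoin-susceptible qualifying uropathogen. Under SAP 5.2 that culture is her baseline and she qualifies. Under SAP Section 4 the specimen is not pretreatment and she does not. If the same urine no longer reaches the qualifying count, both rules leave her out. So under 5.2, but not under Section 4, her inclusion turns on what the first dose did.

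**3. The plan's own figures.** Inputs are 76% success in both arms, a -10 point margin, and 442 per arm at the final analysis (884 / 2) (Protocol 9.2.1), with final boundary Z = 2.23 (SAP Table 2).

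- Standard error = sqrt(2 × 0.76 × 0.24 / 442) = 0.0287.
- Minimal difference = -0.10 + 2.23 × 0.0287 = -0.036, matching the stated -3.6%.
- Two-look power with 530 at the interim, boundaries 2.104 and 2.23 and the interim futility Z of 0.854 applied is 90.2%, matching the stated 90%.

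**4. Size of the selection effect.** The documents give no count of post-dose samples, so every input here is an assumption. Let q be the share of otherwise eligible participants in one arm with only a post-dose culture, a the share of these who fall below the threshold in that arm only, and s the success rate those lost would have had. With w = q × a:

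retained success rate = (0.76 - w × s) / (1 - w)

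| q | a | s | w | Retained rate | Shift (points) |
|---|---|---|---|---|---|
| 1% | 50% | 85% | 0.005 | 0.75575 / 0.995 = 0.7595 | -0.05 |
| 1% | 50% | 95% | 0.005 | 0.75525 / 0.995 = 0.7590 | -0.10 |
| 5% | 50% | 85% | 0.025 | 0.73875 / 0.975 = 0.7577 | -0.23 |
| 5% | 50% | 95% | 0.025 | 0.73625 / 0.975 = 0.7551 | -0.49 |

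The largest of these, 0.49 points, is 0.49 / 2.87 = 0.17 of the final standard error. More extreme assumptions give more: q = 5%, a = 100%, s = 95% gives -1.0 points, and q = 10%, a = 100%, s = 95% gives -2.1 points.

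**5. Direction.** If gepotidacin lowers counts faster, its early responders are the ones lost, its rate falls, and noninferiority becomes harder to show. If nitrofurantoin does, the comparison moves in gepotidacin's favour. The documents do not settle which.

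**6. Cost of the stricter rule in power.** The 884 is a count within micro-ITT NTF-S, so the target does not change. If excluded participants were not replaced, 1% fewer gives N = 875 and power 89.9%; 5% fewer gives N = 840 and power 88.6%.

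**The case against.** The best defence is that the problem should hardly arise. The schedule makes bacteriology a predose procedure, eligibility itself needs a pretreatment urine, randomisation follows the pretreatment assessments, and the first dose is given on site. A post-dose-only culture would be a deviation, and SAP 4.1 reviews deviations affecting population membership before unblinding. Section 4 also still says pretreatment, so the SAP may never admit such a participant. This stands as a reason to expect few cases and a small effect. It does not settle the conflict, because the blinded review has no stated rule for choosing between the two sections. The ME-TOC NTF-S analysis excludes major deviations that prevent efficacy evaluation, but does not name sample timing among them.

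Two stronger readings are tempting, and the documents support neither.

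- A reader might infer that a later post-dose urine could displace a valid predose one. The general rule in 5.2 selects the latest predose value, and the exception speaks of all Day 1 samples without any replacement rule. The SAP is silent on duplicates, which is a gap but not a replacement rule.
- A reader might infer that post-dose symptom scores bias the primary endpoint in the same way. Symptom score is not a criterion for micro-ITT or micro-ITT NTF-S, and clinical success at TOC needs a total score of zero whatever the baseline. A post-dose score mainly moves participants between improvement and worsening, both of which are failures.

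**Conclusion.** The inconsistency is real and should be corrected. For urine cultures, SAP 5.2 contradicts SAP Section 4 and the protocol on who belongs in the primary population, the departure is not declared, and no planned analysis tests it. What is established is that entry could depend on the assigned drug, not that it will.

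Under the central assumptions (1-5% post-dose-only, half of those lost in one arm and none in the other, 85-95% success among those lost) the shift in one arm's rate is about 0.05 to 0.5 points, against a final criterion of -3.6 points. A reader might take the conflict to mean that the primary result is unreliable or tilted towards noninferiority. The documents do not support that: they give no number of affected participants, the direction is open, and shifts of a point or more need nearly all affected participants to be lost, in one arm only, with nearly all of them eventual successes.

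**What to change.** Amend SAP 5.2, for urine cultures only:

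- Take qualifying baseline uropathogens and nitrofurantoin susceptibility from the last urine specimen collected before the first dose, on Day -1 or Day 1. This also settles which sample is used when there are several.
- Keep the assumption that an untimed Day 1 sample is predose.
- Exclude from micro-ITT and its subsets any participant whose only Day 1 urine is documented as post-dose, and report the number by arm.
- Run the inclusive rule as a sensitivity analysis of the primary endpoint.

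The exclusion rests on sample timing and can be applied blind, since SAP Section 4 fixes membership before unblinding. It should be settled before the interim data cut, because the interim set is drawn from the same population. The cost is a wording change and perhaps a few participants leaving the primary population.

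Leave the Day 1 symptom-score convention alone. Under SAP 7.1.1.3 a missing baseline score makes the participant a clinical failure, so discarding post-dose scores would turn cured participants into therapeutic failures. At 76% success, each 1% of an arm affected would lower its rate by about 0.01 × 0.76 = 0.76 points, more than the problem being corrected is likely to cause.

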5.2.1. Qualifying Uropathogens

The algorithm for determining baseline qualifying uropathogens based on microbiology laboratory quantitative culture results is provided in Figure 2 and Section 11.10:

Figure 2 Baseline Algorithm for Determining Qualifying Uropathogens

Only the following uropathogen species/groups, including Gram-negative bacilli (e.g. *E. coli*, *K. pneumoniae*, *P. mirabilis*), *S. saprophyticus*, and *Enterococcus* spp., will be considered for inclusion in the micro-ITT and other microbiological populations.

